Stratum 1 dosing will start with a full dose of nivolumab 3 mg/kg (dose level 1), and one dose de-escalation is allowed; after evaluating dosing for single agent nivolumab then participants will be treated with 240mg of nivolumab and 1mg/kg of ipilimumab will be added to evaluate combination therapy (dose level 2) with one dose de-escalation allowed. No intra-participant dose escalations will be allowed. The safety evaluation period is 6 weeks at a given dose level. Stratum 2 dosing will begin at the single agent therapy maximum tolerated dose (MTD) for Stratum 1 (dose level 1 or -1). Stratum 2 will not be allowed to escalate beyond the MTD for Stratum 1. Only 1 dose de-escalation will be allowed.

The study treatment consists of up to 46 intravenous (IV) infusions of nivolumab on Day 1 of each 2-week cycle for the dose level -1 and 1 cohorts. For dose level 2, IV infusions of nivolumab are given on Day 1 of each 2-week cycle and ipilimumab on Day 1 every 6 weeks, i.e., every third cycle (cycles 1, 4, 7, etc.). For dose level -2, IV infusions of nivolumab are given on day 1 of each 2-week cycle, and ipilimumab

is given on day 1 every 12 weeks, i.e., every sixth cycle (cycles 1, 7, 13, etc.). Participants with an overall response of stable disease (SD), partial response (PR), complete response (CR), or unconfirmed progressive disease (PD) at Week 8 will continue treatment (Refer to Section 9.1 for Response Evaluation Criteria in Solid Tumors (RECIST) Criteria for up to 84 weeks, (42 IV infusions of nivolumab every 2 weeks, see the table below for the ipilimumab schedule if on dose level 2 or -2).

Dose Level	Nivolumab* q2 wk (46 doses)	Ipilimumab**
-1	1mg/kg	-
1	3mg/kg	-
2	240mg	1mg/kg q 6 wk(16 doses)(day 1 of nivolumab cycles 1, 4, 7, 10, 13, 16, 19, 22, 25, 28, 31, 34, 37, 40, 43, and 46)
-2	1mg/kg	1mg/kg q 12 wk (8 doses)(day 1 of nivolumab cycles 1, 7, 13, 19, 25, 31, 37, and 43)

^{*} Treatment will continue until documented disease progression, discontinuation due to toxicity, withdrawal of consent or end of study, up to 46 doses of nivolumab.

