For Stratum 1, the study is a phase I dose de-escalation trial with a rolling six design to establish the MTD for single agent nivolumab and then the MTD for combination of ipilimumab and nivolumab. Since there are only two dose levels within each single and combination therapy, the design requires the full cohort of six participants to be enrolled unless two of the first three participants in that cohort experience a DLT, or if two or more participants in that cohort experience a DLT. In Stratum 1, two agents will be studied, initially nivolumab as a single agent (starting at Dose Level 1) and then the combination of ipilimumab and nivolumab (starting at Dose Level 2 or -2). After evaluating single agent nivolumab dosing, the next dose level will be 2 if dose level 1 is the MTD for single agent nivolumab or dose level -2 if dose level -1 is the single agent MTD. If 2 DLTs are experienced at Dose Levels 1 or 2, then one dose de-escalation (Dose Levels of -1 or -2, respectively) will be permitted according to the dose de-escalation schedule. Fixed doses will be administered according to the dosing schema in the treatment plan. The Phase I MTD for single agent or combination therapy is the dose level at which $\leq 1/6$ participants experience DLT, with the next higher dose having >2 participants encountering DLT (unless the MTD is the highest pre-specified dose level). The safety evaluation period is 6 weeks at a given dose level. No dose escalation will be allowed in an individual participant. and participants who have dose limiting AEs or disease progression will discontinue therapy. During the period for evaluating DLT, participants who withdraw from the study or do not complete the required cycles of treatment owing to reasons other than drugrelated AEs can be replaced. Participants will have blood drawn before each cycle for routine safety laboratory monitoring. All participants will be followed every 2 weeks for treatment administration, exam, toxicity, response, and compliance assessment for a minimum of 8 weeks and up to 92 weeks of treatment.

Table 1: Dose De-Escalation Schedule Stratum 1 and 2

Dose Level	Nivolumab* q2 wk x 46 doses	Ipilimumab**
Level -1	1 mg/kg	-
Level 1	3 mg/kg	-
Level 2	240 mg	1 mg/kg q 6 wk x 16 doses (day 1 of nivolumab cycles 1, 4, 7, 10, 13, 16, 19, 22, 25, 28, 31, 34, 37, 40, 43, and 46)
Level -2	1 mg/kg	1 mg/kg q 12 wk x 8 doses (day 1 of nivolumab cycles 1, 7, 13, 19, 25, 31, 37, and 43)

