^{*}Doses are stated as exact dose in units (e.g., mg/m², mcg/kg, etc.) rather than as a percentage.

***Treatment will continue until documented disease progression, discontinuation due to toxicity, withdrawal of consent, or the study ends, up to 46 doses of nivolumab (with ipilimumab, if receiving).

NOTE: After evaluating single agent nivolumab dosing, the next dose level will be 2 if dose level 1 is the MTD for single agent nivolumab and dose level -2 if dose level -1 is the single agent MTD. It is also possible to de-escalate from dose level 2 to -2. Stratum 2 participants will not be allowed to escalate beyond the MTD for Stratum 1; one dose level de-escalation of the nivolumab and ipilimumab combination or to single agent nivolumab will be allowed based on the doses in the schema in the treatment plan.

NOTE: Participants treated on the cHL cohort and participants on the solid tumor expansion cohort of 24 participants will be treated at 240 mg.

These rules are based on concurrently enrolling up to six participants on the initial dose level (Dose Level 1). However, accrual will be suspended before enrolling the 4th-6th participants on a cohort to until safety has been evaluated in the first three participants, unless at least two participants on that cohort have completed the safety evaluation period without DLT.

- If, after completing the first six weeks for single agent nivolumab (Dose Level 1), none or one participant out of six exhibits a POSSIBLY, PROBABLY or DEFINTELY, study treatment-related DLT (i.e., ≤1/6 participants with DLT at that Dose Level 1; see Section 4.4), then the next cohort of participants will be treated at Dose Level 2.

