- 2. However, if a second participant develops a study treatment POSSIBLY, PROBABLY or DEFINTELY related DLT, even if it is before there are six total participants on that level, then the single agent MTD has been exceeded and no additional participants should be added to this dose. A total of six participants should then be treated on the next lowest dose level (Dose Level -1) to ensure its tolerability and to better define the MTD. Thus, the MTD is defined as the highest assigned dose level at which ≤1/6 participants have a DLT. If ≥2 participants on level -1 experience a POSSIBLY, PROBABLY or DEFINTELY related DLT, the MTD will have been exceeded and no additional participants will be added at level -1 or receive combination therapy levels 2 or -2. If Dose Level -1 is the single agent MTD, then the next cohort of participants will be treated at Dose Level -2.

^{**}When the two drugs are administered, nivolumab will be administered first. Doses of intravenous nivolumab will be administered every 2 weeks up to 46 doses. Ipilimumab will be administered every 6 weeks on dose level 2 or every 12 weeks on dose level -2.

3. If, after completing first 6 weeks for combination of ipilimumab and nivolumab (Dose Level 2 or -2), 0/6 or ≤1/6 exhibits a POSSIBLY, PROBABLY or DEFINTELY, study treatment-related DLT then that dose level is the combination-agent MTD. If a second participant develops a study treatment POSSIBLY, PROBABLY or DEFINTELY related DLT, even if it is before there are six total participants on that level, then the combination-agent MTD has been exceeded and no additional participants should be added to this dose. A total of six participants should then be treated on the next lowest dose level (Dose Level -2 if not already at the lowest dose) to ensure its tolerability and to better define the MTD. If ≥2 participants on level -2 experience a POSSIBLY, PROBABLY or DEFINTELY related DLT, the MTD will have been exceeded and no additional participants will be added at level -2.

4.2.1 Dosing for Stratum 1

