After review of AEs in Stratum 1, this will be followed by evaluation of nivolumab and ipilimumab in Stratum 2. Stratum 2 single agent dosing will begin after the MTD for Stratum 1 single agent therapy has been confirmed (dose level 1 or -1). After the Stratum 1 combination therapy MTD is determined (dose level 2 or -2), Stratum 2 will begin evaluation of combination therapy at that dose level. Up to six participants will be concurrently enrolled at the Stratum 1 MTD, following the dose de-escalation rules and treatment plan outlined above in Section 4.2 and 4.2.1. Stratum 2 participants will not be allowed to escalate beyond the MTD for Stratum 1; one dose level de-escalation of the nivolumab and ipilimumab combination or to single agent nivolumab will be allowed based on the doses in the schema in the treatment plan. The Phase I MTD is the dose level at which <1/6 participants experience DLT with the next higher dose having ≥2 participants encountering DLT (unless the MTD is the highest pre-specified dose level). No dose escalation will be allowed in an individual participant, and participants who have dose limiting AEs or disease progression will discontinue therapy. During the period for evaluating DLT, participants who withdraw from the study or do not complete the required cycles of therapy owing to reasons other than drug-related AEs can be replaced. During the first four cycles of treatment, participants will have blood drawn weekly for routine safety laboratory monitoring. Participants will then be followed every 2 weeks for treatment administration, exam, toxicity, response, and compliance assessment for a minimum of 8 weeks, and up to 92 weeks.

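### Section 4.2.2 starts Stratum 2 combination therapy at Stratum 1's combination MTD and omits the single-agent gate written in Section 4.2; the two texts conflict only if Stratum 2 fails dose level 1

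*Combined protocol and SAP*

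**What the plan says.** Section 4.2.2 sets two starts for Stratum 2. For nivolumab alone, "Stratum 2 single agent dosing will begin after the MTD for Stratum 1 single agent therapy has been confirmed". For the combination, once the Stratum 1 combination MTD has been determined, "Stratum 2 will begin evaluation of combination therapy at that dose level". The next sentence enrols up to six participants at the Stratum 1 MTD, "following the dose de-escalation rules and treatment plan outlined above in Section 4.2 and 4.2.1". The section goes on to cap Stratum 2 at the Stratum 1 MTD and to allow one step down, either within the combination or to nivolumab alone.

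Section 4.2 ties the combination level to the single-agent result:

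- Rule 1: with no more than one DLT in six at level 1, "then the next cohort of participants will be treated at Dose Level 2".
- Note under the dose table: the next level is "dose level -2 if dose level -1 is the single agent MTD".
- Rule 2: with two or more DLTs at level -1, "no additional participants will be added at level -1 or receive combination therapy levels 2 or -2".

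The opening narrative of Section 4.2 is worded for Stratum 1. The dose table is not: it is headed "Table 1: Dose De-Escalation Schedule Stratum 1 and 2". Its note states the gate and in the next sentence names Stratum 2 participants. The same note stands under the two-stratum schedule that follows the protocol schema.

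The other Stratum 2 texts (Synopsis, Sections 4.3.3, 10.1.2 and 10.3) give Stratum 1's MTD as the start or the cap and allow a step down. The Synopsis puts the last point as "Only 1 dose de-escalation will be allowed". Section 2.3.9 reports that level 2 was tolerable in Stratum 1, so the level to which Section 4.2.2 points is now level 2.

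**The concern.** Stratum 2 is run separately because patients with low CD4 counts may be more susceptible to toxicity (Section 10.1.2). A cap at Stratum 1's MTD gives no protection in the case for which the stratum exists, namely that it tolerates less than Stratum 1.

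Suppose two Stratum 2 participants have DLTs on 3 mg/kg nivolumab. Read literally, Section 4.2.2 still opens the combination at level 2. Section 2.3.8 cites FDA simulations that put exposure at 240 mg within 6% of 3 mg/kg. Participants would therefore start at about the nivolumab exposure that their stratum had just failed, with ipilimumab added. The dose-review group in Section 4.4 is bound to apply the protocol's own rules, so those rules should give it one answer.

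**Working it through.** **1. The two instructions side by side.** Stratum 1's combination MTD is taken as level 2 (Section 2.3.9).

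| Stratum 2 single-agent result | Section 4.2.2, literal | Section 4.2 rules and note |
|---|---|---|
| Level 1 cleared | level 2 | level 2 |
| Level 1 failed, level -1 cleared | level 2 | level -2 |
| Both failed | level 2 | no combination |

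They agree in the first row and differ in the other two. The only precedence clause found ranks Section 5.1 over Appendix X and does not bear on this.

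**2. Size of the dose difference.** Level 2 is nivolumab 240 mg every 2 weeks with ipilimumab 1 mg/kg every 6 weeks. Level -2 is nivolumab 1 mg/kg every 2 weeks with ipilimumab 1 mg/kg every 12 weeks. At assumed weights of 60, 80 and 100 kg, 240 mg is 240/60 = 4.0, 240/80 = 3.0 and 240/100 = 2.4 mg/kg. That is 2.4 to 4.0 times the level -2 nivolumab dose, with ipilimumab twice as often.

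**3. Does the sample size settle the reading?** The plan's total reproduces: 18 + 18 + 24 + 24 + 12 = 96 (Section 10.2). With six participants per level, the longest Stratum 2 paths are:

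- Gated rule: levels 1, 2, -2 = 18; levels 1, -1, -2 = 18. Maximum 18.
- Literal rule, one step down per regimen: levels 1, -1, 2, -2 = 24.
- Literal rule, one step down in all: levels 1, -1, 2 = 18.

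The stated 18 matches the gated rule. It also matches the last path, but that path leaves no step down from level 2, which sits badly with Section 4.2.2 and with rule 3 of Section 4.2. The 18 favours the gate without proving it.

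**4. Does timing supply the gate?** No. The trigger in Section 4.2.2 is the Stratum 1 combination MTD alone. If Stratum 2 opens after all of Stratum 1 (Section 4.1), the trigger is already met. Section 10.3 instead opens Stratum 2 after Stratum 1's single-agent part. As an illustration only, assume that Stratum 1 combination and Stratum 2 single-agent enrolment open together, which no text states, at the rates in Section 3.4.2 and with 6 weeks = 1.38 months:

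- Stratum 1 combination: 6/2 + 1.38 = 4.38 months, or 4.76 with the pause before participants 4 to 6.
- Stratum 2 single agent: 6/1 + 1.38 = 7.38 months.
- The trigger comes first by 7.38 - 4.38 = 3.00 or 7.38 - 4.76 = 2.62 months.

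**5. How often would the texts diverge?** They diverge when Stratum 2 has at least 2 DLTs in 6 at level 1. For a true rate p the chance is 1 - (1 - p)^6 - 6p(1 - p)^5. The documents give no p for Stratum 2, so these rates are assumptions:

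| Assumed p | Chance of 2 or more in 6 |
|---|---|
| 5% | 0.033 |
| 10% | 0.114 |
| 20% | 0.345 |
| 30% | 0.580 |

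These are chances that the two instructions part company. They are not chances of misdosing.

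**The case against.** The strongest reply is that the gate already reaches Stratum 2. The note stands under two schedules titled for both strata and names Stratum 2 participants; rules 1 to 3 are not limited to Stratum 1; and Section 4.2.2 itself invokes the Section 4.2 rules. On that view the disputed sentence only says when the combination becomes available and sets its ceiling. Section 10.1.2 also sends the reader to Section 4.2 for the decision rule, and the maximum of 18 fits. Most of this stands, and it makes the gated reading the better one. It does not remove the conflict. Section 4.2.2 fixes where Stratum 2 begins, not how high it may go, and then enrols at Stratum 1's MTD. The rules that it invokes can be taken to govern only what follows that start.

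The second reply is that safeguards prevent harm. Accrual pauses before participants 4 to 6, a second DLT closes the level, and the review group would have seen the single-agent DLTs. This limits the consequence. The pause and the stop act only after dosing has begun, and the group still needs one rule.

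The third reply is that the rates are hypothetical. That is correct. The only level 1 DLT data reported are no DLT in three evaluable Stratum 1 participants (Section 2.3.8), who are few and had higher CD4 counts.

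A reader might infer two stronger things. One is that the plan has no gate for Stratum 2, or directs that a failed dose be given; the note and rule 2 say otherwise. The other is that Stratum 2 is still enrolling, because Section 3.1.10 speaks of enrolment in both strata as yet to be completed. That sentence treats Stratum 1 in the same way, although Section 2.3.9 already reports its combination result. It looks like carried-over text and shows nothing about Stratum 2's status.

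**Conclusion.** The inconsistency is real but narrow. The start level in Section 4.2.2 contradicts the Section 4.2 rules only where Stratum 2 has two or more DLTs at level 1. In that branch the choice is between level 2 and either level -2 or no combination, in the stratum considered more vulnerable. The gated reading is the more likely intent, so this is a sentence that fails to repeat a safety condition, not a design without one. The conclusion rests on Stratum 1's combination MTD being level 2 and on Stratum 2's single-agent result being unreported. If Stratum 2 has already cleared level 1, nothing remains to resolve. The assumed DLT rates and the 2.6 to 3.0 month gap are illustrative and carry no weight in the conclusion. Severity: minor to should-fix.

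**What to change.** Amend Section 4.2.2 to say three things:

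- Stratum 2 combination therapy opens only after Stratum 2's own single-agent evaluation is complete.
- It starts at the lower of Stratum 1's combination MTD and the level that Section 4.2 allows from Stratum 2's single-agent MTD (level 1 to level 2, level -1 to level -2).
- It does not open if level -1 fails in Stratum 2.

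If Stratum 2 has already cleared level 1, a sentence recording that is enough.

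The cost is one or two sentences in an amendment. The maxima of 18 and 96 stand. The downside is a possible delay to Stratum 2 combination enrolment, at planned accrual about 6 + 1.38 = 7.4 months per single-agent level. The Section 4.2 sequence already implies that wait.

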10.1.2 Analysis of primary objective

Please see Section 4.2 of the Treatment Plan for the dose de-escalation decision rule. In summary, the primary goal in this phase I study is to determine the safety and feasibility of ipilimumab and nivolumab in combination therapy in participants with advanced HIV-associated solid tumors, and to determine the maximum tolerated dose (MTD) in this participant population. A rolling design will be used, where successive cohorts of two to six participants will be enrolled into specified dose levels. Dosing from nivolumab alone to nivolumab in combination with ipilimumab will occur according to the scheme in the treatment plan; the safety evaluation period is 6 weeks. The MTD for single agent or combination therapy is the starting dose level at which $\leq 1/6$ participants experience DLT with the next higher dose having at least >2 participants encountering DLT (unless the MTD is the highest pre-specified dose level). DLTs for this protocol are defined in Section 4.4. Given the potential susceptibility of participants with CD4+ counts \(\leq 200 \)/mm³, the dose de-escalation will initially occur in participants with counts >200/mm³ (Stratum 1), and then participants in Stratum 2 (100-200/mm³ CD4 counts) will be evaluated starting at the MTD determined in Stratum 1 after reviewing the safety profile for Stratum 1. For Stratum 2, participants will be enrolled starting at the Stratum 1 DLT in cohorts of 2-6 participants. Stratum 2 participants will not be

allowed to escalate beyond the MTD for Stratum 1; one dose level de-escalation will be allowed based on the criteria in the treatment plan.

If a DLT occurs in none or one participant in Stratum 1 at a particular dose level, a total of six participants will be enrolled to that cohort. If a second participant experiences a DLT, the MTD will have been exceeded. If 2 DLTs are experienced at the first cohort, one dose de-escalation (Dose Level -1) will be permitted according to the study schema in the treatment plan. Similarly, if 2 DLTs are experienced at dose level 2, a dose de-escalation (Dose Level -2) will be permitted. Thus, the MTD is the dose level at which $\leq 1/6$ participants experience DLT with the next higher dose having ≥ 2 participants encountering DLT (unless the MTD is the highest pre-specified dose level) during the safety evaluation period.

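### Section 4.2.2 defines the Stratum 2 MTD by <1/6 DLTs where every other statement accepts ≤1/6, so 1 DLT in 6 gives opposite decisions; separately, a >2 clause leaves a gap in the MTD definition

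*Combined protocol and SAP*

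**What the plan says.** **Acceptance threshold.**

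- The opening paragraph of Section 4.2 puts the MTD at ≤1/6 DLTs, and decision rule 1 moves on after zero or one DLT among six.
- Decision rule 2: "the MTD is defined as the highest assigned dose level at which ≤1/6 participants have a DLT".
- Decision rule 3, for the combination: "0/6 or ≤1/6 exhibits a POSSIBLY, PROBABLY or DEFINTELY, study treatment-related DLT then that dose level is the combination-agent MTD".
- Both definitions in Section 10.1.2 use ≤1/6.
- Section 4.2.2 (Stratum 2) alone differs: "The Phase I MTD is the dose level at which <1/6 participants experience DLT with the next higher dose having ≥2 participants encountering DLT". Earlier in the same paragraph it says that Stratum 2 enrolment follows the rules in Sections 4.2 and 4.2.1.

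**Condition on the next higher dose.**

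- Section 4.2, opening paragraph: "with the next higher dose having >2 participants encountering DLT".
- Section 10.1.2, first definition: "next higher dose having at least >2 participants encountering DLT".
- Section 4.2.2 and the closing definition in Section 10.1.2 use ≥2.
- All these definitions waive the condition at the top planned level.

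**When a level is exceeded.** This is stated one way throughout. Decision rule 2 says of a second DLT: "even if it is before there are six total participants on that level, then the single agent MTD has been exceeded". Section 10.1.2 says: "If a second participant experiences a DLT, the MTD will have been exceeded". Section 4.2 de-escalates on 2 DLTs, and Section 10.1 ends a cohort early at two or more.

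**The concern.** The MTD definition is the decision rule for the primary objective, and the protocol prints it with two acceptance thresholds. On a literal reading, Stratum 2 needs 0 of 6 where Stratum 1 needs 0 or 1 of 6, and no rationale is given for a stricter rule.

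The decision carries forward. Section 3.3 admits participants with CD4 counts of 100 or more to the expansion only if Stratum 2 tolerates the same dose level as Stratum 1. Sections 4.1, 4.2.3, 4.3.3 and 10.1.2 split the expansion if the strata's MTDs differ. Section 3.1.10 still treats completion of Stratum 2 as future, so the sentence in question governs the stratum that the text shows as unfinished.

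The >2 clause raises a smaller problem: it can leave the trial without a level that formally satisfies the definition, even though the decision rules have done their work.

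**Working it through.** **Inputs.** Six participants per level (Sections 4.2 and 10.1); the thresholds set out above; Stratum 1 enrolment of 4 to 18 (Section 10.2). The true DLT rate p is not in the documents. It is assumed to be 10%, 20% or 30%, with 5% to 40% as the outer range.

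**Step 1. Reproduce the stated enrolment.** The maximum is three full cohorts: 3 × 6 = 18. The minimum occurs when Dose Levels 1 and -1 both fail as early as possible, because the combination levels then do not open. If a level closes at its k-th DLT and nobody else has been enrolled by then, the minimum is k + k:

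- second DLT closes the level (≤1/6 acceptable): 2 + 2 = 4, as stated;
- first DLT fails the level (literal <1/6): 1 + 1 = 2;
- third DLT needed (literal >2 used as a closing rule): 3 + 3 = 6.

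Only ≤1/6 with the second DLT exceeding gives four.

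**Step 2. One DLT in six, Stratum 2.** Under decision rules 1 to 3 in Section 4.2 the level is acceptable. Under the literal Section 4.2.2 definition it is not. The decisions are opposite.

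**Step 3. How often that outcome arises.** With all six evaluable, P(0) = (1−p)^6, P(1) = 6p(1−p)^5 and P(≤1) = P(0) + P(1).

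| True rate p | P(0 of 6): accepted if <1/6 | P(1 of 6): wordings disagree | P(≤1 of 6): accepted if ≤1/6 |
|---|---|---|---|
| 10% | 0.531 | 0.354 | 0.886 |
| 20% | 0.262 | 0.393 | 0.655 |
| 30% | 0.118 | 0.303 | 0.420 |

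The last column is computed before rounding. Over 5% to 40%, P(1 of 6) lies between 0.19 and 0.40.

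**Step 4. Two DLTs.** The level itself fails ≤1/6 and <1/6 alike, and every action rule calls it exceeded. Now suppose the level below it has at most 1 DLT in 6. Under ≥2 the lower level is the MTD. Under literal >2, a higher level with exactly 2 DLTs does not satisfy the clause, so no level meets the definition.

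Accrual to a level stops at the second DLT, so a third can come only from participants already enrolled. If all six were always treated, the share of exceeded levels with exactly 2 DLTs would be P(2)/[1 − P(≤1)], where P(2) = 15p²(1−p)^4:

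- 10%: 0.098/0.114 = 0.86;
- 20%: 0.246/0.345 = 0.71;
- 30%: 0.324/0.580 = 0.56.

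Stopping accrual can only raise these shares. Where the clause applies, exactly two is the usual result at an exceeded level.

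**The case against.** **The symbols may not be the authors'.** The text reviewed was extracted from PDF, and ≤ or ≥ can lose its underline. The phrase in Section 10.1.2 that combines a minimum with >2 reads naturally only as ≥2. Similar mixed pairs occur in the cardiac table of Section 5.1, the KS progression criteria in Section 9.2.4 and the Karnofsky cut-offs in Appendix XIII. Against this, ≥2 survives in the same sentence as <1/6 in Section 4.2.2, and ≤1/6 survives beside >2 in Section 4.2. That rules out a uniform loss but not an occasional one. The point stands as a reason to check the source before calling this an author error.

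**Stratum 2 is already governed by ≤1/6.** The <1/6 appears once, no de-escalation rule fires at one DLT, and Section 4.2.2 adopts the Section 4.2 rules. This is good evidence of intent, and a reader who infers that Stratum 2 was deliberately given a stricter rule has no support in the text. It does not remove the conflict, because the definition and the cross-reference stand in one paragraph and disagree.

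**A reader might infer that the exceeding rule is written two ways, so that 2 of 6 gives opposite decisions.** The documents do not support this. Wherever an action is stated, the second DLT exceeds the level. The >2 occurs only as a condition on the next higher dose within a definition, so its effect is the gap in Step 4.

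**The gap has limited reach.** The clause is waived at the top level, Section 2.3.9 reports Stratum 1 Dose Level 2 as tolerable, and the Stratum 2 definition in Section 4.2.2 uses ≥2. What remains for Stratum 2 is the disagreement with the first definition in Section 10.1.2. Sections 4.4 and Appendix VI also leave dose decisions to a group that includes the biostatistician, who would probably resolve it sensibly.

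**Conclusion.** The concern holds in two limited parts.

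1. In Stratum 2, exactly 1 DLT in 6 passes or fails a level depending on which sentence is followed. At assumed true DLT rates of 10%, 20% and 30% that outcome has probability 0.35, 0.39 and 0.30, and the chance of accepting the level is 53%, 26% and 12% under the literal wording against 89%, 66% and 42% under ≤1/6. A literal reading could make the strata's MTDs appear to differ and so change who enters the expansion, and how.
2. The >2 in Section 4.2 and in the first definition of Section 10.1.2 leaves a formal gap below a level with exactly 2 DLTs. No level is wrongly accepted because of it.

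The figures assume independent DLTs at a common rate and six evaluable participants. The finding assumes that the symbols are as printed, which this text cannot settle. It is an inconsistency in how a decision threshold is stated, not a flaw in the design: the numbered rules in Section 4.2 are coherent and agree with the stated minimum. It merits correction but is not a critical defect.

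**What to change.** Check the source file for lost underlines at the three places: the opening paragraph of Section 4.2, Section 4.2.2 and the first definition in Section 10.1.2. If the symbols are as printed, reconcile those definitions with the numbered decision rules in Section 4.2, so that one acceptance threshold and one next-higher-dose condition appear throughout. Those rules are the version consistent with the Stratum 1 minimum of four in Section 10.2. If a stricter Stratum 2 threshold was in fact intended, the cross-reference to Section 4.2 would have to change and a rationale be given.

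In the same edit, reconcile the sentence in Section 10.1.2 that starts Stratum 2 at the Stratum 1 DLT with the sentence before it, which says MTD.

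The cost is a few symbols and one word in an amendment. Aligning to the Section 4.2 rules leaves Stratum 1 enrolment at 4 to 18.
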